
At 6 months after disclosure...

Primary Hypothesis 1.1: ADCS-PACC scores will be lower among A+D+ participants than A+D- participants.

Exploratory Hypothesis 1.2: African-Americans will demonstrate a higher level of neuropsychological bias in response to amyloid imaging results than other racial groups due to complex sociocultural reasons which can negatively influence cognitive testing outcomes.

Specific Aim #2: To determine whether disclosure of elevated brain amyloid will cause psychological distress.

At 6 months after disclosure...

Secondary Hypothesis 2.1: A+D+ participants will have greater IES scores than A-D+ or D- participants.

Exploratory Hypothesis 2.2: A+D+ participants will have higher scores on scales of subjective memory complaints than A+D- participants.

Exploratory Hypothesis 2.3: Comparison of outcomes at 6 weeks and 6 months after disclosure will show African-Americans to be equally vulnerable to psychological distress after amyloid imaging as other racial and ethnic groups.

Specific Aim #3: To explore how learning amyloid imaging disclosure will impact preventative health behaviors, advance planning for health (e.g. long-term care insurance decisions) and well-being (e.g. stigma, quality of life and relationships).

Specific Aim #4: To examine whether disclosure of amyloid levels affects performance by inducing stereotype threat.

At 6 months after disclosure...

Quaternary Hypothesis 4.1: The effects of disclosure on task performance will depend upon whether or not the test is described as assessing cognition.

Quaternary Hypothesis 4.2: The effects of disclosure on pupil dilation (a measure of effort and

arousal that is assumed to index stereotype threat) will depend upon whether or not the test is described as assessing cognition.

III. Subject Selection

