Eligible participants will be cognitively and neuropsychiatrically normal, fluent English speakers, between the ages of 65-80, who have at least one first-degree relative with AD, are willing to undergo blinded (undisclosed) *APOE* genotyping, and are willing to participate in the randomized trial of amyloid imaging disclosure. Participants will be excluded if they have suffered a stroke or head trauma, have active medical or psychiatric illness that is unstable or progressive, or are taking acetylcholinesterase inhibitors or memantine. Participants with a history of anxiety or depression that has resolved or that has been treated and is stable will be enrolled. Formal documentation of AD family history will not be required as our previous REVEAL studies have demonstrated the reliability of self-reported family history of AD.

The inclusion and exclusion criteria for this study include assessment of participants' mood, especially symptoms of depression and anxiety, and persons who score above cut-off scores will be excluded. In addition, measures of depression and anxiety are endpoints of the study as well as measures of safety. We will decide participants' eligibility based on conversations between the study staff (clinician judgment) and participant, as well as pre-specified cut-off scores in screening measures to identify persons in need of additional monitoring:

- Geriatric Depression Scale (GDS) (range 0 to 15): > 10 exclude. 6-10 additional monitoring/use discretion on whether to enroll

- State-Trait Anxiety Inventory (STAI) (range 6-24): ≥ 19 exclude. 17-18 increased monitoring.

- Columbia Suicide Severity Rating Scale (CSSRS): Exclude any serious suicidal risk (investigator judgment)

To have a sufficient number of elevated amyloid participants for the planned analyses, we will enrich the participant pool with additional AD dementia risk factors. Age and having the *APOE* $\epsilon 4$ genotype are robustly associated with amyloid positivity and approximately 24% of unselected individuals will be $\epsilon 4+$. Our experience in the REVEAL Study has indicated that among persons who self-identify as having a first-degree family member with AD, the percentage of individuals who are $\epsilon 4+$ increases to about 47%. Thus, we will restrict participation to those who have such a family history.

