The first neuropsychological test battery will be performed at this Visit #2. Baseline cognitive status will be ascertained using the Alzheimer's Disease Cooperative Study Preclinical Alzheimer Cognitive Composite (ADCS-PACC) to ensure the participant is cognitively normal.⁴⁴ The ADCS-PACC is comprised of measures of episodic memory (Buschke Selective Reminding Test, Logical Memory I, II), timed sensorimotor function (Digit Symbol Subtest from the WMS), and a global test of cognition (MMSE). Pre-specified cut-off scores of safety screening measures are listed under the "Safety of Participants" section below.

In addition to the ADCS-PACC, the neuropsychological test battery is also comprised of 1) a test of effort: Test of Memory Malingering (TOMM)⁴⁵, 2) a measure of attention and short-term memory capacity: Digit Span forward span test⁴⁶ and 3) a test of premorbid function (TOPF)⁴⁷

After the neuropsychological battery is the full education session. To assess participants' knowledge prior to the education session, we will ask the participant a list of questions on a "Pre-Education" checklist. Participants will then receive a full educational session about Alzheimer's disease dementia risk factors, amyloid imaging, and the meaning of an elevated and not elevated result in an older adult with normal cognition. The content of this written description was generated using a modified Delphi consensus process that involved experts in human amyloid imaging and informed consent for genetic testing. It includes sections that describe what is amyloid, what is Alzheimer's disease, how do we know whether someone has brain amyloid, what does having a brain amyloid scan involve, what does a positive brain amyloid scan mean, is a positive amyloid scan like other medical risks, and what a negative brain amyloid scan means. The participant is allowed to ask questions regarding the information just learned. After the educational session, the participant will complete a "Post-Education" checklist.

The NEO personality index,⁴⁸ Geriatric Depression Scale (GDS),⁴⁰ Mini-State Trait Anxiety Inventory (Mini-STAI),⁴¹ and Columbia Suicide Severity Rating Scale (CSSRS),⁴² are then administered to the participant to assess for signs of depression and anxiety (see "Inclusion/Exclusion Criteria" section for cut-off scores).

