Pre-specified cut-off scores of safety screening measures are listed under the "Safety of Participants" section below. Those found to be cognitively or emotionally impaired will be offered appropriate referral. Should safety be a concern, the disclosure provider or study coordinator will schedule additional in-person visits or phone calls as needed or make a referral to a mental health professional as indicated.

Step 10— Visit #5: 6-Week Follow-Up + Neuropsychological test battery + Secondary Outcome Measures + Cognitive Measures + Health Behavior Surveys

Participants will return in-person six weeks (Visit 5) post-disclosure. The neuropsychological battery, consisting of the 1) ADCS-PACC as our primary outcome measure to assess neuropsychological status,⁴⁴ 2) TOMM,⁵⁵ 3) Digit span forward test⁴⁶ TOPF⁴⁷ will be administered.

The secondary outcomes measures at six weeks will measure anxiety and depression with the GDS,⁴⁰ mini-STAI,⁴¹ and CSSRS measures⁴²; test-specific distress with the Impact of Events Scale (IES)⁵⁴; psychological impact of risk disclosure with the adapted INI-AD; quality of life with the SF-12 measure⁵¹; and perceived time with the Future Time Perspective scale.⁵²

Subjective cognitive measures of the Metamemory in Adulthood (MIA),⁴⁹ Memory Function Questionnaire (MFQ),⁵⁰ and Cognitive Function Instrument (CFI)⁵⁶ will be administered.

Participants will also take the follow-up health behavior surveys to determine the type and frequency of behavior changes in response to learning risk information. Information

collected will include assessing health behavior changes, advanced planning, insurance changes (i.e. purchasing or altering long-term care policies), medication changes, willingness to enroll in clinical research, stigma, and tolerance of research risk.

In addition, Dynamic Experiments for Estimating Preference (DEEP)⁶¹ behavioral assessments will measure participant risk and time preference as presented electronically through various decision-making scenarios.

Step 11 – Visit #6: 6-Month Follow-Up + Neuropsychological test battery + Secondary Outcome Measures + Cognitive Measures + Health Behavior Surveys + Additional Stereotype Threat Measures

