The secondary outcomes measures at six months will measure anxiety and depression

with the GDS,⁴⁰ mini-STAI,⁴¹ and CSSRS measures⁴²; test-specific distress with the Impact of Events Scale (IES)⁵⁴; psychological impact of risk disclosure with the adapted INI-AD; quality of life with the SF-12 measure⁵¹; perceived time with the Future Time Perspective scale⁵², Essentialist Beliefs about Aging Question⁶³, and a question about feelings of stereotype threat about Alzheimer's disease risk..

Subjective cognitive measures of the Metamemory in Adulthood (MIA),⁴⁹ Memory Function Questionnaire (MFQ),⁵⁰ and Cognitive Function Instrument (CFI)⁵⁶ will be administered.

Participants will also take the follow-up health behavior surveys to determine the type and frequency of behavior changes in response to learning risk information. Information collected will include assessing health behavior changes, advanced planning, insurance changes (i.e. purchasing or altering long-term care policies), medication changes, willingness to enroll in clinical research, stigma, and tolerance of research risk.

In addition, Dynamic Experiments for Estimating Preference (DEEP)⁶¹ behavioral assessments will measure participant risk and time preference as presented electronically through various decision-making scenarios.

Finally, the Everyday Discrimination Scale⁶² has been developed and will be used to assess perceived discrimination at Visit 6.

Step 12 – Visit #7: Delayed Amyloid Scan Disclosure for Initial D- Group

At the end of study data collection, participants in the control arm will return in-person (Visit 7) within approximately four weeks after their 6-month follow-up to learn their amyloid imaging results.

Step 13 – Phone Call #5 for initial D- Group after delayed disclosure: 1-3 Day Safety Check

Participants initially randomized to be in the delayed non-disclosure (D-) group, who later learn their amyloid imaging scan results at Visit #7 will be called by the study coordinator in 1-3 days to assess the participant's status as a safety check. Psychological impact of the disclosure visit will be measured by using the adapted Impact of NeuroImaging for Alzheimer's Disease (INI-AD) scale.⁵³

VI. Biostatistical Analysis

Data Collection

Data will be collected by the study coordinator and project manager, and monitored by the PI. The PI will be responsible for monitoring and assuring the validity and integrity of all data and adherence to the IRB approved protocol.

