Should a serious adverse event (e.g., self-inflicted physical harm due to receipt of test results, severe acute depression or anxiety attributed to receipt of test results, etc.) occur, the investigator at that site would notify the co-PIs and the multidisciplinary Data Safety and Monitoring Board via email immediately following the event. They would review the case in question and additional study data as needed to make recommendations as to how we can improve the safety of the study, or if the study needs to be halted.

Ensuring Safety of Human Subjects

In previous REVEAL Study clinical trials that have involved disclosure of AD dementia genetic risk information, we have developed the following detailed and documented procedures for reducing risks to participants that we have adapted for this study that will involve the disclosure of amyloid imaging.

In addition to careful and thorough communication with potential participants around the consent process, we have several layers of protection built into this protocol that have adequately guarded against any adverse consequences to date. These include:

- A. Pre-screening of all participants for clinically significant depression and anxiety.
- B. Careful education defining amyloid imaging and the meaning of amyloid imaging results.
- C. Scheduled follow-up visits after disclosure of PET amyloid imaging result with standardized rating scales for affect and anxiety. Additional monitoring and appropriate actions will be taken based on conversations between the study staff (clinician judgment) and participant, as well as pre-specified cut-off scores in screening measures:
 - Impact of Events Scale (IES): >25 increase monitoring
 - Geriatric Depression Scale (GDS) (range 0 to 15): >10 exclude. 6-10: Increase monitoring at investigator discretion and look at change from previous score
 - State-Trait Anxiety Inventory (STAI) (range 6-24): ≥ 19 exclude. 17-18 Increase monitoring at investigator discretion and look at change from previous score
 - Columbia Suicide Severity Rating Scale (CSSRS): Exclude any serious suicidal risk, based on investigator's judgment, can be followed up by site designated mental health professional and increase monitoring

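### The post-disclosure safety list says *exclude* for high GDS, high STAI or suicidal risk; probably carried-over screening wording, but literal use would remove randomised participants because of endpoint scores

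*Protocol*

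**What the plan says.** Item C of Ensuring Safety of Human Subjects (protocol section VII) opens with "Scheduled follow-up visits after disclosure of PET amyloid imaging result with standardized rating scales for affect and anxiety". It is separate from item A, which covers pre-screening. Its list gives four rules:

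- IES above 25: more monitoring, nothing else.
- GDS: ">10 exclude. 6-10: Increase monitoring at investigator discretion and look at change from previous score".
- STAI: exclude at 19 or more; monitor at 17 to 18.
- CSSRS: exclude serious suicidal risk on the investigator's judgment, with mental-health follow-up and more monitoring also allowed.

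The lead-in bases action on clinician judgment as well as on the cut-offs. The Psychological risks paragraph at the start of section VII likewise places cut-off scores for affect and anxiety at the scheduled visits after disclosure.

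Section III (Subject Selection) uses the same GDS and STAI cut-offs for enrolment; its GDS rule is "> 10 exclude. 6-10 additional monitoring/use discretion on whether to enroll". The same section says that "measures of depression and anxiety are endpoints of the study as well as measures of safety". For Visit 6 the protocol states "The secondary outcomes measures at six months will measure anxiety and depression", using the GDS, mini-STAI and CSSRS.

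For distress after disclosure the protocol elsewhere prescribes something other than removal. Step 9 says "Those found to be cognitively or emotionally impaired will be offered appropriate referral".

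**The concern.** *Exclude* has a plain meaning before randomisation. After it, the word could mean stopping visits, stopping some procedures or discarding data, and neither document says which. The mood scales are endpoints as well as safety measures, so a rule that removes people for a high score selects on the outcome. If disclosure distresses one group more, that group loses more of its most distressed members, and what remains looks calmer than it was.

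Three comparisons are exposed: the 6-month IES contrast in protocol Secondary Hypothesis 2.1 ("A+D+ participants will have greater IES scores than A-D+ or D- participants"), the time-averaged IES contrast in SAP Analysis 2.1, and the 6-month GDS and STAI results. Each would move toward no harm, in a trial meant to find out whether disclosure does harm.

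**Working it through.** The plan gives no figure on this point, and no rate at which participants cross a cut-off after disclosure. The check is therefore a comparison of the texts, followed by an illustration on assumed inputs.

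**1. Does the list apply after disclosure?** Item C's heading and the Psychological risks paragraph both say so, and the list includes the IES, which is scheduled only after disclosure. Two other features prove less.
- Steps 5 and 9 both state "Pre-specified cut-off scores of safety screening measures are listed under the" safety section further down. Step 9 is the 1-3 day call, which uses only the INI-AD and the IES intrusion subscale, so among the listed rules only the IES one could apply there.
- The instruction to look at change from an earlier score could also fit Visit 2, because GDS and STAI are already taken at Visit 1.

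**2. When could exclusion first bite?** GDS, STAI and CSSRS are first repeated after disclosure at Visit 5 (6 weeks), the visit at which the 6-week IES is collected. Exclusion then would cost the 6-month data. The SAP's main IES contrast, at 6 weeks, changes by 0% unless data already collected are dropped.

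**3. Does other text settle the meaning?** Section IX takes the same STAI threshold, 19 or more, and has it recorded, reported to the PI within a week and followed up. Its GDS threshold is 12 or more, so a GDS of 11 meets *exclude* in item C without meeting the GDS adverse-event trigger. Section IX also has the clinician see each participant at 6 weeks and 6 months, and section VII (Minimizing Risks, item D) describes referral and continuing contact. These passages conflict with *exclude*, but none says how the word is to be read. Continued safety monitoring in section IX concerns people who withdraw or cannot complete cognitive tests, not people excluded on a mood score. SAP Aim 2 takes all study participants and does not address anyone stopped for a score.

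**4. Illustration for the 6-month IES.** Assumed:
- IES gamma-distributed with shape 1, mean 10 in A+D+ and 7 in A-D+ at both visits (true ratio 10/7 = 1.43, log ratio 0.357).
- Correlation of IES between visits 0.6.
- Correlation ρ of 6-week mood with 6-week IES 0.5 or 0.7 (Gaussian copula).
- Anyone above a mood cut-off at 6 weeks has no 6-month IES.

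Simulation with 2 million per group, comparing visit means (equivalent to a gamma log-link GEE with independence working correlation):

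| Removed, A+D+ vs A-D+ | Ratio, ρ = 0.5 | Ratio, ρ = 0.7 | Fall in log ratio |
|---|---|---|---|
| 1% vs 0.5% | 1.42 | 1.42 | 1.2% to about 1.7% |
| 5% vs 2% | 1.40 | 1.39 | 5.2% to about 7.8% |
| 8% vs 3% | 1.39 | 1.37 | 8.1% to about 11.7% |

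The time-averaged log ratio falls by about 0.6% to 6%. Letting the between-visit correlation run from 0.4 to 0.8 widens the 6-month range to 0.7% to 16.5%. With exchangeable working correlation (60,000 per group) the 6-month log ratio runs from 0.5% larger to 1.4% smaller. The SAP does not say which structure it will use.

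**5. Scale against sampling error.** Using 370 participants, 1:1 allocation, about 10% dropout and roughly 30% A+:
- A+D+: 370 × 0.5 × 0.9 × 0.30 = 50.
- A-D+: 370 × 0.5 × 0.9 × 0.70 = 117.
- With gamma shape 1, the standard error of the log ratio is √(1/50 + 1/117) = 0.169.
- Largest shift in the table: 0.357 × 0.117 = 0.042, which is 0.042/0.169 = 0.25 standard errors.

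**6. Illustration for 6-month GDS/STAI.** For cut-off c with share q above it, the 6-month share above c among those kept is 1 − Φ₂(c, c; r)/(1 − q), where Φ₂ is the bivariate normal distribution function and r = 0.6 is the assumed mood correlation between visits.
- 1% vs 0.5% becomes 0.82% vs 0.43%: difference 0.5 to 0.4 points.
- 5% vs 2% becomes 3.63% vs 1.57%: 3.0 to 2.1 points.
- 8% vs 3% becomes 5.55% vs 2.28%: 5.0 to 3.3 points.

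At r from 0.4 to 0.8 the difference shrinks by 10% to 54%, that is by 0.05 to 2.7 points.

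**The case against.** The best defence is that nobody would follow the word literally. The cut-offs match the enrolment list, the lead-in invokes clinician judgment, the IES never triggers exclusion, and the CSSRS line itself goes on to follow-up and monitoring. Section IX gives the same STAI threshold a reporting action, and sections V, VII and IX speak of referral and continued visits. The SAP has no mood-score exclusion, and its Aim 2 methods generally follow Aim 1, which includes an ITT analysis using data from people who drop out. Most of this stands, and it is why the expected effect is small. It does not remove the conflict: the word sits under a post-disclosure heading and no text overrides it.

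It is also fair that the exposed results are not the leading ones. The SAP centres Aim 2 on 6 weeks and names IES and INI-AD, not GDS or STAI, as its outcomes; the endpoint status of the mood scales rests on the protocol. Finally, the SAP, dated April 2021, already describes the 6-month visits in the past tense, so rewording the protocol then would change little conduct. The SAP statement and the counts by group would still be useful.

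**Conclusion.** The concern holds as a low-severity wording fault: a rule placed after disclosure uses a screening term, leaves it undefined for randomised participants and conflicts with the follow-up text elsewhere. Read literally, it would bias three non-primary comparisons toward no harm. The size is unknown, probably small, and zero if sites keep participants. Every exceedance rate, IES mean and correlation in the illustration is assumed; only the group sizes come from the documents. The low end is more plausible, because participants are screened on the same GDS and STAI cut-offs and the protocol reports that severe distress was rare in the earlier studies.

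Three stronger inferences are tempting and not supported:

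- That distressed participants will be, or were, removed. The documents show an ambiguous word, and most of the surrounding text points to retention.
- That the SAP's main distress result is compromised. The 6-week IES is collected at the first visit where the rule could bite.
- That the primary PACC comparison suffers. The documents give no link between mood scores and PACC, and lost numbers alone matter little: with a difference of 1.25 and SD 2.2, t-test power goes from 80.3% at 50 vs 50 to 79.5% at 48 vs 50.

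**What to change.** In protocol section VII, item C, limit *exclude* to the period before randomisation. After disclosure, replace it with: refer, increase monitoring, and keep in follow-up unless the participant withdraws. The clinical response itself is for the sponsor to decide.

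In the SAP, state that no randomised participant and no collected data are dropped because of a post-disclosure GDS, STAI, CSSRS or IES score. Report by group the number above each cut-off and any discontinuations for that reason, so that readers can see whether anyone was removed.

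Bringing the GDS thresholds in item C and section IX into line is optional tidying. The cost is a few words in the protocol and a short SAP statement, with no extra visits or participants.

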Based on this calculation, we have set a target to enroll n=50 in each of the 2 elevated amyloid groups (A+D-, A+D+). Due to a much lower than anticipated rate of amyloid positivity and a dropout rate of approximately 10%, we plan to enroll 370 total participants and achieve 100 completed 6 month visits to reach our group enrollment targets of n=50 for each elevated amyloid group.

VII. Risks and Discomforts

Psychological risks: We recognize that persons with normal cognition who learn they have elevated amyloid and an increased risk of developing AD dementia could experience psychological distress. We will monitor psychological well-being in our participants by pre-screening potential participants for anxiety and depression and administering standardized rating scales with pre-specified cut-off scores for affect and anxiety at scheduled follow-up visits after disclosure of PET amyloid imaging results. Additional monitoring and appropriate actions will be taken based on conversations between the study staff (clinician judgment) and participant.

For the 6-month visit digit-span task, we will examine how memory performance is affected by task instructions. Although the purpose of all the included cognitive measures is to assess the link between amyloid status and performance, during this task we will explicitly state this

relationship. Although we expect this to increase concerns about task performance, we do not expect this to create emotional distress. However, we will monitor responses. This will be done via conversations between the study staff (clinician judgment) and participant.

Deception: Mild deception will be used during the 6-month visit digit-span task. More specifically, during the initial trials of this task participants will be told that the purpose is to calibrate the equipment. No calibration will be conducted, but this instruction will reduce any evaluative concerns that may be felt by the participants. We do not anticipate this mild deception to create any distress. However, participants will be fully debriefed about this at the end of the study and their questions will be answered.

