There is no direct benefit from participating in this study. This is not a treatment study, and participants will not receive any medication. By participating REVEAL-SCAN, participants may be eligible to participate in other research studies.

Trials that require disclosing AD biomarker results to cognitively normal older adults may present the prospect of empowering people to action beyond research participation, such as adopting healthy behaviors and lifestyle changes, but they may also cause harm to both perceived and actual cognitive performance, mood, and social and personal well-being. Prior

data from the REVEAL Study suggests that the information that subjects learn may decrease their anxiety about developing AD (or about their close friend, relative or spouse' chance of developing AD) or may allow individuals to make long-term decisions for the future.^{53,58-60}

The results of our study will be first-of-their kind data to measure whether such harms are real, and, if they are, their magnitude and severity. This knowledge will be of substantial importance to AD investigators, clinicians and healthcare policy makers, and, therefore, we believe the risks to the participants are reasonable and justified.

IX. Monitoring and Quality Assurance

The risks of the study are outlined above. The study clinician/project manager will be responsible for the monitoring of participant outcomes, under the supervision of the PI. Frequent contact with the study clinician, both by phone and in person at the designated follow-up sessions, will be our primary source of clinical participant monitoring. Participants will be contacted by phone within 1-3 days of receiving their AD risk assessment in order to check in on their emotional state and answer any questions regarding the information or the study itself. At minimum, the study clinician will also meet with each participant for in-person follow-ups 6 weeks and 6 months after receiving their risk assessment. At each of these follow-up appointments, the study clinician will also review participants' mood screening measures and other survey responses in real time in order to help look for possible adverse psychological reactions.

Additionally, at minimum, the study clinician will monitor safety through the completion of mood scales, review participants' mood screening measures and other responses in real time in order to help look for possible adverse psychological reactions.

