Quality control for standardized ADCS-PACC administration via audio recordings will be shared with Duke University via secure file sharing. Sites will only provide the study personnel's name performing the ADCS-PACC, and label the recording with subject ID numbers, not with names or any other identifiable information.

Non-serious Adverse Events will mostly include events in which participants exceed thresholds on the anxiety or depression scales ($GDS \geq 12$; $Mini-STAI \geq 19$), and will be recorded and reported within 1 week to the PI for review and appropriate follow-up, and reported to the IRB and Data Safety and Monitoring Board annually.

An interim analysis may be conducted by the Data Safety Monitoring Board (DSMB). They will review the study on an annual basis.

Review of Adverse Events

Study site personnel must report immediately to the principal investigator any adverse events from this study. Should a serious adverse event (e.g., self-inflicted physical harm due to receipt of test results, severe acute depression or anxiety attributed to receipt of test results, etc.) occur, the investigator at that site would notify the co-PIs and the multidisciplinary DSMB via email immediately following the event. They would review the case in question and additional study data as needed to make recommendations as to how we can improve the safety of the study, or if the study needs to be halted.

If, for some reason, a participant withdraws or is unable to complete cognitive assessments, the Investigators will discontinue him or her undergoing detailed cognitive batteries. Where possible, safety monitoring procedures will be conducted until the end of the study.

During all portions of this research study, the privacy and confidentiality of all participants will be maintained at all times. All hard copies of research data will be kept in the study clinician's locked office. Data will be stored in locked filing cabinets, in binders, and on the study staff members' computers. Digital files of audio recordings will be labeled only with subject ID numbers, not with names or any other identifiable information. This data is accessible only by research staff, primarily the PI and study staff. The code linking the study ID with the identifiers will be stored on the study clinician's computer in a password protected computer file. Only the password protected file will contain the link between the identifiers and the study ID.

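### The adverse-event trigger for depression (GDS 12 or more) sits one point above the protocol's own GDS safety limit (above 10), so a post-disclosure score of 11 is not automatically reported

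*Protocol*

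**What the plan says.** Three parts of the protocol set a GDS cut-off.

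- **Entry (section III, Subject Selection):** "Geriatric Depression Scale (GDS) (range 0 to 15): > 10 exclude. 6-10 additional monitoring/use discretion on whether to enroll".
- **After disclosure (section VII, Ensuring Safety of Human Subjects, item C):** "Geriatric Depression Scale (GDS) (range 0 to 15): >10 exclude. 6-10: Increase monitoring at investigator discretion". Item C opens with "Scheduled follow-up visits after disclosure of PET amyloid imaging result with standardized rating scales for affect and anxiety", so this list applies after randomization as well as at screening.
- **Adverse-event reporting (section IX, Monitoring and Quality Assurance):** non-serious events are mostly those whose scores "exceed thresholds on the anxiety or depression scales ($GDS \geq 12$; $Mini-STAI \geq 19$), and will be recorded and reported within 1 week". Such events go to the PI within a week and to the IRB and DSMB once a year.

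The STAI cut-off is 19 or more in all three places. GDS is collected after disclosure at the 6-week visit (section V, Step 10: "The secondary outcomes measures at six weeks will measure anxiety and depression with the GDS") and again at the 6-month visit (Step 11).

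**The concern.** Psychological distress is the first risk the protocol lists, and section III treats the depression and anxiety scales as safety measures as well as endpoints. The number that defines a depression adverse event should therefore agree with the number the protocol uses as its depression limit, unless a reason for the difference is given. None is.

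A participant could learn an amyloid result, score 11 at follow-up, and so pass the level at which the protocol would have refused entry, without any score-based adverse-event record being required. For that score, the one-week report to the PI and the annual report to the IRB and DSMB depend on individual judgment. The clinical sites could record the same score differently.

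The score would probably not go unnoticed. What is at stake is the automatic link between the depression limit and the count of adverse events that the oversight bodies see. The SAP does not close the gap, because its distress aim (Aim 2) names IES and INI-AD as outcomes and not GDS.

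**Working it through.** No sample-size, power or alpha figure is involved. The check compares the integer scores that satisfy each rule.

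| Scale (range) | Entry limit, section III | Post-disclosure limit, section VII item C | Adverse-event trigger, section IX | Over the limit but below the trigger |
|---|---|---|---|---|
| GDS (0–15) | >10: 11–15 | >10: 11–15 | ≥12: 12–15 | 11 |
| STAI (6–24) | ≥19: 19–24 | ≥19: 19–24 | ≥19: 19–24 | none |

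For GDS, {11, 12, 13, 14, 15} minus {12, 13, 14, 15} leaves {11}. For STAI the sets are identical. The mismatch is therefore one score on one scale.

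**How many scores this could involve.** The inputs from the documents are the enrolment and dropout figures in section VI, Power Calculation ("a dropout rate of approximately 10%, we plan to enroll 370 total participants") and the two post-disclosure GDS assessments per participant.

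- Upper bound on assessments, nobody lost: 370 × 2 = 740.
- Lower bound, all of the 10% lost before 6 weeks: 370 × 0.90 = 333, and 333 × 2 = 666.

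The documents do not give the share of assessments scoring exactly 11. Taking 0.1% to 1% as an assumed range:

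- At 0.1%: 666 × 0.001 = 0.67 to 740 × 0.001 = 0.74.
- At 1%: 666 × 0.01 = 6.7 to 740 × 0.01 = 7.4.

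That gives about 0.7 to 7 scores across the trial. Because anyone above 10 is excluded at entry, an 11 requires a rise after screening, so the true number could be zero.

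**After the change.** With the trigger at >10, both GDS rules cover 11–15 and no score falls between them.

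**The case against.** The strongest reply is that the cut-offs do different jobs. Section III decides eligibility, section VII item C guides monitoring and action, and section IX defines what is logged and reported. Acting at one score and reporting at a slightly higher one is a coherent scheme, and nothing says the figures must be equal. The post-disclosure benchmark is also imprecise: item C says only that scores above 10 are excluded, without defining exclusion for someone already randomized.

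The safeguards at a score of 11 are real. At each follow-up the study clinician reviews "mood screening measures and other survey responses in real time in order to help look for possible adverse psychological reactions". Item C lets clinical judgment prompt action at any score, and section VII provides for referral to a site clinician. The adverse-event definition is open-ended, so an 11 may still be reported, and the value stays in the data set in any case.

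Much of this stands. The participant is unlikely to be missed, and the estimated count rests on an assumed share. The two-tier reading, however, has no support in the text. For anxiety the trigger equals the safety limit, and only depression departs from that pattern. The other safeguards do not make reporting automatic, which is the purpose of a numerical trigger. The general duty in section IX to report every adverse event to the PI does not help either, because it leaves open whether an 11 is an adverse event. A deliberate choice of 12 cannot be ruled out, but the protocol would then need to say so.

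**Conclusion.** The concern holds. The protocol gives two different upper cut-offs for depression, and a post-disclosure GDS of exactly 11 exceeds the safety limit without meeting the adverse-event trigger. That much follows directly from the text.

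The practical reach is small: one score value, and about 0.7 to 7 observations if 0.1% to 1% of 666 to 740 assessments fall on it. That share is an assumption, and zero is possible. What is lost is automatic recording and oversight reporting; the clinical review remains. Endpoint, alpha, power and sample size are unaffected. It is still worth correcting, because it concerns a safety rule for a main risk of the trial and costs very little to put right.

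**What to change.** In section IX, replace the GDS figure of 12 or more with GDS above 10 (11 or more), so that the depression trigger matches sections III and VII as the anxiety trigger already does. If 12 was intended, add a sentence giving the reason and stating how a score of 11 is to be handled. The same amendment could usefully say what exclusion means in item C for a participant who has already been randomized.

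The SAP, dated April 2021, describes Covid-19 as affecting the end of the study. If follow-up is complete, the equivalent step is to list the post-disclosure GDS scores of 11 and report them alongside the adverse events.

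The cost is one changed figure with the usual IRB review of a minor amendment, and possibly a few more non-serious reports (about 0.7 to 7 under the assumption above). No analysis changes.
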